### **2.1.3 Date of first/last administration of study drug**

The date of first administration of study drug is derived as the first date when a non-zero actual dose of study drug was administered as recorded on Dosage Administration Record (DAR) Electronic Case Report Form (eCRF). The date of first administration of study drug will also be referred as ‘start of study treatment’.

The date of last administration of study drug is defined as the last date when a non-zero actual dose of study drug was administered as recorded on DAR eCRF. This date will also be referred as ‘last date of study treatment’.

### **2.1.4 Study day**

The study day **for safety** (e.g. adverse event onset, laboratory abnormality occurrence, vital sign measurement, Electrocardiogram (ECG), etc.) will be calculated using the start date of study treatment as the reference. For assessments occurring

- **on or after the start date of study treatment**, the study day will be calculated as (date of safety assessment) – (start date of study treatment) + 1. Study day 1 will therefore be the first day of study treatment.
- **before the start date of study treatment**, the study day will be calculated as (date of safety assessment) – (start date of study treatment).

For example, if an adverse event starts 3 days before the start of study treatment the study day displayed on the listing will be negative, i.e. -3.

The study day will be displayed in the data listings.

### **2.1.5 Baseline**

Baseline is considered as the result of an investigation describing the ‘true’ uninfluenced state of the patient.

For **safety evaluations** (e.g. laboratory, vital signs, etc.) the last available (i.e. non-missing) assessment before or on the date of start of study treatment is taken as ‘baseline’ value or ‘baseline’ assessment.

If patients have no value as defined above, the baseline result will be missing. Unscheduled assessments will be considered in the determination of baseline.

For safety assessments, if an assessment is planned to be performed prior to the first dose of study drug in the protocol and the assessment is performed on the same day as the first administration of study drug, it will be assumed that it was performed prior to study drug administration, if assessment time point is not collected or is missing.

Patients who start treatment and discontinue from the study on the same day may have 2 different sets of data collected on study Day 1, one being reported to the week 1 visit, the other reported to the End Of Treatment (EOT) visit. Data reported at the EOT visit are not eligible for baseline selection.

For analyses of the entire granule period requiring comparison to baseline value (e.g. lab shift tables, pubertal staging etc.) the baseline is defined as follows. For patients randomized to DT formulation who switched to granule formulation in the extension phase, the date of the last assessment prior or equal to the start date of granules in the extension phase will be defined as pre-granule value which will be reference value for changes in the extension time. For patients randomized to granules continuing in extension phase the initial baseline value at study start will be taken.

### **2.1.6 On-treatment period**

The overall observation period will be divided into three mutually exclusive segments taking into account stop rules as per [Table 2-1](#):

- Pre-treatment period: from day of patient's first informed consent to the day before first dose of study drug;
- On-treatment period: from day of first dose of study drug to 30 days after last dose of study drug.
- Post-treatment period: starting at day 30+1 after last dose of study treatment.

For the entire granule period, the following conventions will be taken into account while deriving the three observation periods above:

- For patients enrolled in DT formulation in the core phase, the pre-treatment period will not be derived, and their entire granule period starts from Extension phase start date mentioned in [Table 2-1](#)
- For patients enrolled in Granule formulation in the core phase, the first dose of study drug will be the day of first dose in the core phase.

### **2.2 Analysis sets**

The Safety Set 1 will consist of all ICT naïve patients (as per eCRF) who received at least one dose of the study drug during the core phase.

The Safety Set 2 will consist of all ICT pre-treated patients (as per eCRF) who received at least one dose of study drug during the core phase.

The Safety Set 3 will consist of all patients who received at least one dose of study drug during the core phase.

Safety set 1 to 3 will only be used for the analysis of lens photography (LOCSIII) and color fundus photography. Safety set 3 is only used for disclosure related analysis, deaths and drug

dispensation listings. Both assessments were only collected since protocol amendment 6 which was implemented after the EoC CSR.

All analysis for the final CSR will be based on Safety Set 4.

The Safety Set 4 will consist of all patients who received at least one dose of granule formulation during the core or extension phase.

Patients will be analyzed according to the treatment actually received and strata information recorded in the eCRF.

Treatment actually received is defined as the treatment the patient received at the first day of study medication in the core phase

## **Protocol deviations**

Frequency counts and percentages of patients with any protocol deviation (selection criteria not met, patient not withdrawn as per protocol, treatment deviation, prohibited concomitant medication, other Good Clinical Practice (GCP) deviation) will be tabulated by the deviation type category and treatment arm on the Safety Set 4 for the entire granule period. Patients with COVID-19 related protocol deviations will be presented separately in the table.

The full list of protocol deviations is documented in the Validation And Planning (VAP) Module 3 document. The COVID-related protocol deviations and relationship to pandemic will be identified and maintained in an independent tracker located in the document management system in the “CREDI Studies/ICL670F2202/TMF (Study Level)/Protocol Deviations” folder. The latest available tracker prior to database lock will be used.

All protocol deviations and COVID related protocol deviations will be listed on Safety Set 4.

## **2.3 Patient disposition, demographics and other baseline characteristics**

### **2.3.1 Patient disposition**

Listings will be produced on the Safety set 4 with a flag for extension phase data.

The summaries of patient disposition during the extension phase by treatment arm on the Safety Set 4 will show:

- Number (%) of patients who entered in the optional extension phase;
- Number (%) of patients who were not treated during the optional extension phase;
- Number (%) of patients who were treated during the optional extension phase;
- Number (%) of patients who completed the optional extension phase;
- Number (%) of patients who discontinued the optional extension phase;
- Number (%) of patients for each reason for optional extension phase discontinuation

### 2.3.2 Demographics and other baseline characteristics

All patients' demographic and baseline characteristics as well as enrollment status by region, country, center and treatment arm were analyzed for the primary CSR analysis and will not be repeated for the final CSR.

Demographics, disease characteristics and baseline characteristics will only be generated for safety set 4 subjects as defined in the SAP from primary analysis.

## 2.4 Treatments (study treatment, rescue medication, concomitant therapies, compliance)

Safety Set 3 will be used for drug dispensing listing.

### 2.4.1 Study treatment

Listings will be produced by treatment arm on the Safety Set 4.

Definitions of duration of exposure, total patient-years exposure, average daily dose, cumulative total dose as well as percentage of planned dose taken are defined in [Table 2-2](#):

**Table 2-2 Deferasirox: Study drug exposure**

Overall duration of exposure (day):	$[(\text{date of last exposure}) - (\text{date of first study treatment}) + 1]$
Overall duration of exposure (months)	$[(\text{date of last exposure}) - (\text{date of first study treatment}) + 1]/30.4375$
Drug exposure on dose X (days)	$[(\text{date of last exposure on dose X}) - (\text{date of first study treatment on dose X}) + 1]$
Total patient-years (years):	Overall duration of exposure (days) / 365.25
Average dose (planned and actual, in mg/kg/day):	Mean dose over all days between first and last dose, excluding interruptions: sum of all (X dose * corresponding duration of exposure on dose X) / overall number of dosing days
Cumulative dose (planned and actual, in mg/kg):	Sum over daily doses of all days between first and last dose
Percentage of planned dose taken:	$100 \times [\text{Cumulative actual dose} / \text{Cumulative planned dose}]$

For patients who switch from DT to granules in the extension phase, date of last exposure of study drug in core phase refers to the day prior to the date of the first administration of granules in extension phase (including a zero actual dose) as defined in [Table 2-1](#).

For patients who switch from DT to granules, the date of the first administration of study drug (granules) refers to the first date of granules in the extension phase (including a zero actual dose) to account for treatment interruptions due to efficacy and safety reasons. The last exposure of the granules refers to the last date when a non-zero actual dose of granules was administered during the study extension phase as defined in [Table 2-1](#).

For patients receiving granules throughout the study, the date of the first administration and last exposure of study drug refer to the first and last dates respectively when a non-zero actual dose of study drug (granules) was administered during the study.

Overall duration of exposure and total patient-years will be summarized by treatment arm for the entire granule period.

The following variables will also be summarized by treatment arm and for each phase as appropriate as:

- Duration of exposure will be categorized in the entire granule period as: <6 months, 6-<12 months, 12-<24 months, 24-<36 months, 36-<48 months and so on.

The actual dose in mg/kg/day will be obtained by dividing the actual total daily dose administered in the DAR eCRF page by the last available weight at the time of dose administration reported in the vital signs eCRF page. Average dose, average dose categories (<10.5 mg/kg/day Granule, 10.5-<17.5 mg/kg/day Granule, 17.5-<24.5 mg/kg/day Granule, ≥24.5 mg/kg/day Granule), cumulative dose and percentage of planned dose taken will only be analyzed for patients with complete dates (for all records of the patient) in DAR panel. Patients with complete DAR start and end dates for all the records of the treatment within the granule formulation will be flagged in the listings.

In addition, the number of patients who have any dose interruptions or dose changes with the corresponding reasons will be summarized as collected in the DAR panel.

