**Table 6-2 Criteria for interruption and re-initiation of Deferasirox treatment**

Dose modifications for deferasirox	
Body weight	
Increase/decrease of weight by >10% compared to Visit 3 (baseline weight) or body weight at last dose adjustment due to change in patient's body weight	Dose of study medication needs to be adapted using Dosing Table (provided in Appendix 14.2 ). Only when weight changes with >10% compared to baseline weight or body weight at last dose adjustment due to change in patient's body weight, dose needs to be adapted. Smaller variations in body weight (<10%) during study, does not require adjustments in dose. In this case, baseline body weight can be used to calculate correct dose.
Investigations (Renal)	
Serum creatinine and/or creatinine clearance	
Single increase in serum creatinine $\geq 33\%$	Maintain dose level and repeat the assessment at next visit as clinically indicated
For pediatric patients: - Single increase $\geq 33\%$ above baseline value (visit 3/week1) and $> \text{ULN}$  For adult patients: - Increases by 33% or more above the baseline (visit 3/week1) measurement, repeat the serum creatinine within 1 week, and if still elevated by 33% or more	Deferasirox dose reduction by 10 mg/kg/day for the DT and by 7 mg/kg/day for the granules is necessary.
	If after a dose reduction, a progressive increase in serum creatinine beyond the ULN is observed, a treatment interruption is mandated. If after dose reduction/interruption, resolution of serum creatinine occurs ( $< 33\%$ ) at the next study visit and within normal limits, dose can be resumed again at 100%. If increase in serum creatinine reoccurs again within 2 months according to guidelines above, therapy needs to be reduced to 50% of the last dose. After 2 months, if the serum creatinine increase does not recur, study medication can be returned to 100% of the last dose.
Creatinine clearance between 40 and less 60 mL/min	Reduce dose with 50%. If after dose reduction, resolution of creatinine clearance occurs ( $> 60 \text{ ml/min}$ ), dose can be resumed again at 100%.
Creatinine clearance $< 40 \text{ mL/min}$ or serum creatinine increases $> 2$ times the age-appropriate ULN	Deferasirox therapy must be discontinued

Dose modifications for deferasirox	
Investigations (Hepatic)	
Isolated direct (conjugated) Bilirubin elevation	
> ULN – 2 x ULN	Maintain dose level

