### **10.3 Treatments (duration of exposure, concomitant therapies, percentage of planned dose taken)**

The following variables will be summarized with descriptive measures separately for the Safety Set-1, Safety Set-2, Safety Set-3 and Safety Set-4 by formulation: duration of exposure, in weeks and in categories (core phase: <4 weeks, 4-<12 weeks, 12-<20 weeks, 20-<28 weeks, 28-<36 weeks, 36-<44 weeks,  $\geq$ 44 weeks and extension phase: <6 months, 6-<12 months, 12-<24 months, 24-<36 months, 36-<48 months,  $>$ 48 months); average planned (mg/kg/day) and average actual daily dose; cumulative planned (mg/kg) and total actual dose (mg/kg); percentage of planned dose taken; frequency of interruptions, decreases and increases in planned dose, overall and by reason for change as recorded in the eCRF.

The total patient-years while on treatment, calculated as the sum of (overall drug exposure) / 365.25 will be provided by formulation.

The duration of exposure, defined as the number of weeks (core phase) / months (extension phase) between the start and end of study medication, will be summarized by formulation and by phase. The end of study medication day is the last day with a non-zero actual dose of study medication as recorded on the drug administration pages.

The average daily dose (planned or actual, in mg/kg) is calculated as the mean dose over all days between first and last dose, excluding interim days with zero dose (interruptions). The cumulative dose is calculated as the sum over the daily doses of all days between first and last dose. The current weight is used when calculating the actual daily dose.

The percentage of planned dose taken is derived as  $100 * \text{cumulative actual dose (mg/kg)}/\text{cumulative planned dose (mg/kg)}$ .

Prior and concomitant medications and significant non-drug therapies will be summarized through frequency tables according to their WHO ATC class and WHO generic term by phase. Prior medications are defined to be drugs taken prior to the first dose of study medication. Concomitant medications are medications taken between the first day of study medication and up to 30 days after the last day with study medication or medications starting prior to the first day of study medication and continuing after the start date of study medication.

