## 14.2 Dosing tables (Deferasirox DT, Deferasirox granules)

For each patient the investigator and/or pharmacist will calculate a target daily dose taking into account patient's body weight at randomization. When the calculated dose cannot be reached with the deferasirox tablet / stick pack strengths available, the closest daily dose available will be prescribed. The following dosing tables provide an efficient combination of tablet / stick pack strengths reaching a certain daily dose for each body weight range.

Examples illustrating this approach are provided below:

- For a patient with a body weight of 46 kg and a deferasirox DT dose of 20 mg/kg/day, the calculated daily dose is 920 mg. Taking into account the available DT strengths of 125, 250 and 500 mg deferasirox, the closest daily dose the patient can receive is 875 mg, by taking 3 deferasirox tablets: 1 x 125 mg + 1 x 250 mg + 1 x 500 mg. This combination can be found in the 'Tablets' column, for patients receiving 20 mg/kg/day of deferasirox DT and with a body weight between 41-46 kg.
- For a patient with a body weight of 46 kg and a deferasirox granules dose of 14 mg/kg/day, the calculated daily dose is 644 mg. Taking into account the available stick pack strengths of 90, 180 and 360 mg deferasirox, the closest daily dose the patient can receive is 630 mg, by taking 3 stick packs: 1 x 90 mg + 1 x 180 mg + 1 x 360 mg. This combination can be found in the 'Stick packs' column, for patients receiving 14 mg/kg/day of deferasirox granules and with a body weight between 42-48 kg.

These dosing tables have been constructed for each dosing group using lower and upper body weight limits of 5 and 140 kg, respectively. This is taking into account that the study will enroll male or female children and adolescents,  $\geq 2$  and  $< 18$  years. However, for some patients with a low body weight (e.g. below 19 kg in the 5 mg/kg/day dosing group) the dosing requirements given in [Section 6.1.1](#) will not allow for the use of the smallest strength available (Eg: 125 mg for DT, or 90 mg for granules). In such cases a written request will be sent to Novartis, to advise on the individual patient enrolment / dose adjustments options.

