## 5.3 Time windows

### 5.3.1 Study drug exposure

Study drug will be dispensed at randomization (week 1), then every four weeks. Dose adjustments based on safety are allowed at any time point during the study.

Information on study drug strength will be collected on the Dose Administration Record (DAR) eCRF and includes the planned dose (mg/kg/day), actual total daily dose (mg) taken, reason for the dose change, start date and end date.

[Table 4-3](#) shows the defined study periods for drug exposure.

All assessments within a time period will be used to calculate the drug exposure for the corresponding period.

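### Percentage of planned dose taken mixes recorded intake with whole-unit rounding and growth, and the final SAP computes it only for a complete-date subset that its table of changes does not list

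*SAP*

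**What the plan says.** **The ratio.** Protocol 10.3 defines it as 100 times cumulative actual dose over cumulative planned dose, both in mg/kg. Table 2-2 (study drug exposure) repeats this in the primary SAP and end-of-core SAP (both section 2.6) and in the final SAP (section 2.4.1). The cumulative dose is: "Sum over daily doses of all days between first and last dose".

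**Numerator.** The final SAP obtains the actual daily dose by "dividing the actual total daily dose administered in the DAR eCRF page by the last available weight at the time of dose administration". The two earlier SAPs have the same rule, and Protocol 10.3 agrees: "The current weight is used when calculating the actual daily dose".

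**Denominator.** Final SAP 5.3.1 says that the information on the dose administration record (DAR) "includes the planned dose (mg/kg/day), actual total daily dose (mg) taken, reason for the dose change, start date and end date". For this ratio, no document converts the plan into the whole-unit milligrams prescribed, or ties it to the weight used for dosing.

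**How doses are set.** Protocol 14.2 says that when the calculated dose cannot be made up from the available strengths, "the closest daily dose available will be prescribed". On weight, Protocol Table 6-2 says: "Smaller variations in body weight (<10%) during study, does not require adjustments in dose".

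**Who is analysed.** In final SAP 2.4.1, "percentage of planned dose taken will only be analyzed for patients with complete dates (for all records of the patient) in DAR panel". The same sentence covers average dose, average-dose categories and cumulative dose. Section 5.1.1 imputes the last administration date but no other DAR date. Table 4-1 has one entry, on exposure-adjusted adverse event incidence.

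**The concern.** The name of the statistic invites the reading that 90% means one tenth of the prescribed drug was not taken. But the numerator carries the rounded milligrams and today's weight, while the denominator carries neither. A child dosed exactly as the protocol directs can score well above or below 100.

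The risk of misreading is greatest in the extension. Protocol 7.2.1 and 7.2.3 stop the unit count and the diary there, so no count-based compliance figure exists to set beside this percentage. These are growing children followed for up to five years.

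The date rule raises a different question. One incomplete date removes the whole patient from four dose summaries. A patient with more records has more chances to be removed, so the analysed subset may not represent everyone exposed.

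**Working it through.** **Inputs.** Strengths are multiples of 125 mg (DT) and 90 mg (granules); nominal starting doses are 20 and 14 mg/kg/day (Protocol 6.1.1). Dosing bands are in Protocol Tables 14-4 and 14-5, and the 10% weight rule is in Table 6-2. Weight bands below are whole kilograms, chosen for illustration.

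**1. The protocol's example (14.2).**
- Granules: 46 x 14 = 644 mg; nearest multiple of 90 is 630 mg.
- DT: 46 x 20 = 920 mg; nearest multiple of 125 is 875 mg.

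Both match the protocol.

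**2. The ratio in factors.** Let d be the planned mg/kg, D the dispensed mg, W0 the dosing weight, W the current weight, and f the share of the dispensed dose recorded as taken. The daily score is

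P = 100 x f x (D / W) / d = 100 x f x [D / (d x W0)] x [W0 / W],

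that is, intake times rounding times growth.

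**3. Rounding alone (f = 1, W = W0).**
- 46 kg granules: 630 / 644 = 97.8%. DT: 875 / 920 = 95.1%.
- 16 kg granules (Table 14-5): 180 / 224 = 80.4%. DT (Table 14-4): 375 / 320 = 117.2%.
- 10 kg granules: 180 / 140 = 128.6%.
- Over 10-30 kg: 80.4-128.6% for granules at 14 mg/kg, and 83.3-125.0% for DT at 20 mg/kg.

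| Weight, granules 14 mg/kg | Range | Mean over weights |
|---|---|---|
| 10-19 kg | 80.4-128.6% | 103.1% |
| 20-34 kg | 87.7-111.8% | 99.9% |
| 35-54 kg | 91.8-107.1% | 99.8% |
| 55-74 kg | 94.8-105.2% | 100.2% |

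Rounding is large for individual small children but mostly averages out across weights.

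**4. Growth alone.** At the 10% limit, W0 / W = 1 / 1.10 = 0.909. The 46 kg granules child falls from 97.8% to 88.9% with every unit taken; the DT child falls from 95.1% to 86.5%. For comparison, 90% intake with no growth gives 0.90 x 97.8 = 88.0% on granules. The two are almost indistinguishable. Weight gain only lowers the score, so it does not average out.

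The 0.909 is the floor for a single day, whereas the reported ratio is cumulative. If weight rises steadily from W0 to 1.10 W0 before the dose is recalculated (an assumption), the average of W0 / W is ln(1.10) / 0.10 = 0.953, a fall of about 5%.

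**5. Intake.** For the 46 kg granules child without growth, f = 100, 90, 80 and 50% gives 97.8, 88.0, 78.3 and 48.9%.

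**6. Date rule.** The documents give neither the rate of partial dates nor the number of records per patient. As an illustration only, assume that each record independently has an incomplete date with probability p = 1% (range 0.5-2%). The chance of exclusion with k records is 1 - (1 - p)^k: about 5% (2.5-10%) for k = 5, and 26% (14-45%) for k = 30.

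**The case against.** The strongest reply is that this is an exposure measure and correct as one. A 16 kg child given 180 mg against a 14 mg/kg plan received 180 / 16 = 11.25 mg/kg, and a child who outgrows a fixed dose does receive less per kilogram. Current weight is a proper basis for exposure. That stands. A reader might infer that the tables would show under- or over-dosing that never happened. They would not: the mg/kg departure is real, and what is wrong is to read it as missed doses.

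A reader might also infer that the ratio reflects rounding and growth instead of intake. Step 5 contradicts this, because recorded intake enters in direct proportion. Nor does record quality alter what the ratio measures; it alters who is analysed.

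Three further limits stand:
- Final SAP 2.1.2 confines study drug to granules, so the contrast between formulations at one body weight concerns the protocol and the earlier core-phase tables, not the final report.
- The widest percentages come from small children near the edges of dosing bands.
- The date rule does not touch duration of exposure, patient-years, or the counts of patients with interruptions or dose changes. That it selects patients with few dose changes is plausible but not shown.

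The objection does not answer the absence of any weight-free intake figure in the extension, or the silence of Table 4-1. The primary and end-of-core SAPs already compare actual mg with a calculated planned mg, with a 15% margin, when flagging dose reductions and increases. The percentage has no such allowance.

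**Conclusion.** The point holds in a limited form. Percentage of planned dose taken is mg/kg dose intensity: recorded intake multiplied by a rounding factor and a growth factor. It cannot be read as the share of the prescribed dose that was taken. With full intake, rounding moves a small child's score by up to about 20 points down or 29 points up at 14 mg/kg, and by a few points in heavier children. Permitted growth lowers a daily score by up to about 9%. The proportionality to intake assumes that the planned dose stays above zero on interrupted days, which the documents do not state.

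The complete-date restriction is new in the final SAP: it is absent from Protocol 10.3 and the two earlier SAPs, and undeclared in Table 4-1. Its wording is also unsettled. One sentence requires complete dates on all of a patient's records; the next flags completeness within granule treatment only. The number excluded and any bias are unknown.

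These are descriptive summaries with no test or decision attached. Compliance as a co-primary endpoint is a count ratio (Protocol 10.4.1) and is untouched. The matter should be corrected for interpretation; it does not threaten the trial's conclusions.

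**What to change.** 1. **Add a weight-free ratio.** Report 100 x mg taken / mg prescribed, summed over days. Take the prescribed whole-unit daily dose from the eCRF, where Protocol 6.1.1 requires prescribed doses to be recorded, or derive it from planned dose, dosing weight and Tables 14-4 and 14-5. Rounding and growth then cancel: 100, 90 or 80% intake gives 100, 90 or 80% at any weight. Keep the existing ratio, labelled as mg/kg dose intensity affected by rounding and weight change.
2. **Handle dates per record.** Close a partial end date at the day before the next record starts, and do the reverse for a partial start date. Drop only records that cannot be dated, and report the numbers of records and patients affected by arm. State whether DT core-phase records count, and list the change in Table 4-1.

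The cost is SAP wording, additional derivation code and a footnote to the percentage in past study report tables. Deriving prescribed milligrams takes more work if they are not held as a field, since the DAR contents listed in final SAP 5.3.1 name planned mg/kg and actual mg only. No new data collection is needed.
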